**University of Maryland, Shock Trauma Center
Department of Orthopaedics**

**Impact of Surgery on Pain in Lateral Compression Type Pelvic Fractures:
A Prospective Trial (Pelvis RCT)**

NCT02605766

University of Maryland IRB Number: HP-00060038

Principal Investigator: [name]

Safety Monitor: [name]

Version 4

June 1, 2016

TABLE OF CONTENTS

Protocol Summary	3
Key Roles.....	4
Background Information.....	4
Rationale	5
Potential Risks	5
Potential Benefits	6
Primary Outcome	6
Secondary Outcomes	6
Exploratory Outcomes	6
Description of the Study Design	6
Primary Endpoint	7
Secondary Endpoints	8
Study Population	10
Adjudicating Eligibility	11
Co-Enrollment Guidelines	11
Recruitment.....	11
Study Treatments	11
Clinical Evaluation.....	12
Participant Interviews	13
Study Schedule.....	13
Assessment of Safety	15
Data Analysis	16
Randomization	17
Data Management.....	17
Missing Data	18
Research Ethics Approval.....	18
Informed Consent.....	19
Vulnerable Populations.....	20
Participant Confidentiality	20
Study Discontinuation.....	21
Reports	21
Study Records Retention.....	21
Supporting Literature	21
APPENDIX A	23
APPENDIX B	23
APPENDIX C	See Attachements
APPENDIX D	See Attachements

PROTOCOL SUMMARY

Title	Impact of surgery on pain in lateral compression type pelvic fractures: a prospective trial
Short Title	Pelvis RCT
Type of Study	Prospective randomized control trial OR observational outcomes study
Primary Objective	To determine if surgical stabilization of lateral compression type pelvic fractures decreases patient reported pain at 2 weeks post injury compared to non-operative management.
Secondary Objective	To explore associations between treatment and: 
 1. Patient reported pain up to 1 year post injury 2. Hospital length of stay 3. Time to first mobilization (bed to chair) 4. Narcotic use up to 1 year post injury 5. Work productivity & activity impairment up to 1 year post injury 6. Health related quality of life up to 1 year post injury 7. Pelvic specific functional outcome up to 1 year post injury 8. General function up to 1 year post injury
Sample Size	We will recruit a sample size of 130 patients (65 per arm) with a minimum of 2 week follow-up for the primary outcome
Diagnosis and Main Inclusion Criteria	Lateral compression type pelvic fracture amendable to both operative or non-operative treatment per surgeon opinion in patients between the ages of 18 and 80 years of age, inclusive.
Length of Follow-up	1 year

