PRIMARY OBJECTIVE

To compare 2-week post-injury assessments of patient reported pain of participants undergoing operative versus non-operative treatment following a lateral compression type pelvic fracture. We hypothesize that there will be a decrease in the Visual Analog Scale (VAS) pain scores in the operative group as compared to the non-operative group both during their hospital stay and in the short-term outpatient follow up.

SECONDARY OBJECTIVES

To compare assessments of narcotic use up to 1 year post injury of participants undergoing operative versus non-operative treatment following a lateral compression type pelvic fracture. We hypothesize that there will be a decrease in the narcotic requirements in the operative group as compared to the non-operative group throughout the 1 year follow up.

To compare assessments of time to first mobilization (bed to chair) with physical therapy of participants undergoing operative versus non-operative treatment following a lateral compression type pelvic fracture. We hypothesize that the operative group will mobilize out of bed to chair with physical therapy faster than the non-operative group.

EXPLORATORY OBJECTIVES

To explore associations between treatment and:

1. Hospital length of stay (index hospitalization)
2. Work productivity and activity impairment up to 1 year post injury
3. Health related quality of life up to 1 year post injury
4. Pelvic specific functional outcome up to 1 year post injury.

DESCRIPTION OF THE STUDY DESIGN

The Pelvis RCT study is a prospective randomized treatment trial to evaluate outcomes among operative versus non-operative lateral compression type fractures. If the patient does not agree to randomization, the patient will be asked to participate in the observational arm of the study. A schematic representation of participant enrollment can be found in the figure below.

A total of 130 patients will be enrolled (65 per arm). University of Maryland, Shock Trauma Center will act as the coordinating center for this study and all patient will be recruited from

University of Maryland, Shock Trauma Center and Indiana University Health Methodist Hospital.

Patients and/or the patient's legally authorized representative (LAR) will be approached for informed consent as soon as is feasible following determination of eligibility.

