CO-ENROLLMENT GUIDELINES

If allowed by the local IRB, participants in the Pelvis RCT study may be co-enrolled in other research studies based on the following guidelines:

- A. Regardless of whether the participant is enrolled in the randomization arm or the observational arm of the Pelvis RCT study, the participant may be co-enrolled in any other observational study.
- B. If the participant is enrolled in the randomization arm, he or she may only be co-enrolled in up to two additional randomized control trials prior to the completion of the intervention.
- C. If the participant is enrolled in the randomization arm, he or she may co-enrolled in any other randomized control trial after the intervention is complete.
- D. If the participant is enrolled in the observational arm, he or she may be co-enrolled in any other randomized control trial at any time.

RECRUITMENT

Approximately 130 participants will be enrolled in the Pelvis RCT study. Participants will be recruited during the index hospitalization for the treatment of a qualifying lateral compression type pelvic injury. Consenting procedures are described in detail in the Study Schedule and Informed Consent Sections of this protocol.

STUDY TREATMENTS

Both treatment options used in the study are current standard of care practices and the same resources (pain management, social work, physical therapy, etc.) will be available to study patients as to all trauma patients.

Non-operative Treatment Group

Patients enrolled in the non-operative treatment group will not undergo surgical intervention for their pelvic fracture. They will mobilize as per the surgeon's instructions according to standard of care for this injury. X-rays will be taken at follow-up clinic appointments to determine if the injury is healing properly or if the pelvis has shifted and may warrant surgical intervention. If complications arise and/or surgery is required, crossover will be allowed and recorded within study follow-up forms.

Operative Treatment Group

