During the index hospitalization, participants will be asked about the following:

- Age, gender, race and ethnicity, and education
- Smoking history
- Previous injuries (specifically pelvis or back)
- Pain medication usage prior to this injury
- Work and health status prior to this injury
- General and pelvic function prior to this injury

Follow-up Interviews

At 2 weeks, 6 weeks, 3 months, and 1 year following their injury, participants will be asked about the following:

- Any re-hospitalization or outpatient surgery since the last visit for any reason related to his/her pelvic injury
- Rehabilitation received
- Pain medication usage
- Work Status – Work Productivity and Activity Impairment
- Pain – Brief Pain Inventory
- Health Status – VR-12
- Pelvic Function – Majeed Pelvic Score

STUDY SCHEDULE

Screening and Consent

All patients between the ages of 18 and 80 (inclusive) with a lateral compression type pelvic fracture will be screened for eligibility by the research coordinator or research team members in close coordination with the surgeon investigators. Screening will typically occur within the first day after hospital admission. An eligibility checklist form will be completed on every potentially eligible participant and entered onto the electronic data capture system. The treating surgeon will be available via pager to answer questions regarding study eligibility. When the treating surgeon is not available, the study PI will be available to page. Contact information for the PI and alternate contact is available in Appendix A. In most cases, questions should be resolved at this level.

Once eligibility has been confirmed, the informed consent process will be completed by the research coordinator or research team member and attending surgeon. Patients will be approached about potential participation in the study as soon as is feasible following determination of eligibility. It will be important to enroll these participants as soon as possible to prospectively collect information about their injury and its treatment.

Following completion of informed consent, the participant's study injury characteristics will be further adjudicated by a non-treating surgeon as described in the Adjudicating Eligibility Section of this protocol. Participants with injuries that are not judged eligible for inclusion will be withdrawn from the study.

Enrollment/Baseline

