Our primary hypothesis is that the operative treatment group will have lower VAS pain scores compared to the non-operative treatment group both during their hospital stay and in the short-term outpatient follow-up.

Based on the results of a pilot study, we expect pain scores in the non-operative group to have a mean of 5.7 and a standard deviation of 2.3. Assuming a 20% reduction in pain scores, 130 patients (65 per arm) are required to have an 80% chance of detecting, as significant at the 5% level, a decrease in the primary outcome measure from 5.7 in the control group to 4.56 in the experimental group. This is our primary outcome and the study will be powered for this variable.

Primary data analysis will involve direct comparison of the change in value of the reported pain scores at the time points listed below. We will be powered to detect a 20% reduction in pain. Secondary analysis will compare the value of narcotics administered at the distinct time periods. Tertiary analysis will be comparing the time (in days) to mobilization with physical therapy. The previous retrospective pilot study incorporated a propensity factor, generated from well documented sources of pain. As this is a prospectively randomized trial, we do not anticipate needing to accommodate for matching.

RANDOMIZATION

Eligible patients will be randomized in equal proportions to one of the two treatment groups: 1) operative treatment of the lateral compression type fracture, 2) non-operative treatment of the lateral compression type fracture. Allocation will be concealed using a centralized 24-hour computerized randomization system, www.randomize.net, that will allow Internet based allocation. The treatment allocation will be stratified on the following prognostic factors to ensure balance between the intervention groups: 1) patient intubation status at time of enrollment, 2) patient prescription pain medication usage during the month prior to injury.

DATA MANAGEMENT

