Quality control quality assurance procedures will be in place for the duration of the study. Ongoing data edits and internal audits will be performed to ensure collection of quality data. The continuous and timely flow of data from the AFs and CRFs to the REDCap electronic data capture system is an essential prerequisite for maintaining data quality.

Monthly performance reports will be completed by the coordinating center research coordinator summarizing among other things: recruitment, status of follow up, data completion, and timelines of data entry.

Missing data queries will be reported on the monthly basis by the research coordinator. The research team will be asked to answer these queries as soon as possible. Any unresolved queries will continue to be reported on the monthly basis.

MISSING DATA

As with most prospective studies, missing data will be unavoidable, even with excellent follow up. Since the informative nature of missing data cannot be verified from the observed data, we will adopt a sensitivity analysis framework for reporting results. We will analyze data under a variety of modeling assumptions regarding how strongly the missingness mechanism is related to outcomes. Regarding study conduct, we will:

1. Limit participant burden and inconvenience in data collection
2. Select high quality research team members
3. Monitor and report missing data rates during the study
4. Emphasize the importance of full participation in the study during the consent process
5. Collect information on the reasons for missing data
6. Actively engage participants in the study and educate them about the importance of their engagement
7. Collect surrogate information on participants who miss clinic visits
8. Hold regular meetings to discuss strategies for enrollment and engagement of participation

While these efforts will help to minimize missing data, we recognize that missing data is inevitable.

RESEARCH ETHICS APPROVAL

This protocol, the consent form template, the AFs, and the CRFs have been reviewed and approved by University of Maryland Institutional Review Board (IRB). The protocol, clinical site-specific informed consent forms, and any participant recruitment material will need to be reviewed and approved by each clinical site's local ethics board. Prior to commencement of the

study the clinical site must provide the coordinating center with a copy of the ethics board approval.

INFORMED CONSENT

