**Pelvis RCT: Impact of Surgery on Pain in Lateral Compression Type Pelvic Fractures**

**NCT: 02625766**

**December 28, 2020**

### Statistical Analysis

[figure not shown]
The primary analyses were based on the intent-to-treat principle. The primary analysis for pain and secondary analysis for functional outcome estimated the difference in the average treatment effect based on a longitudinal assessment within the initial 12-weeks after the fracture. This approach uses each patient's multiple outcome assessments to compare the average pain and function experienced over the 12-week period between the treatment groups. For these analyses, we used a Bayesian hierarchical model that applied a prior probability of no treatment difference based on the conflicting evidence in the prior literature [3-6]. This is akin to an initial assumption that there is "no difference" in pain or functional outcome between the treatment groups. In addition to estimating the average treatment effect, we calculated the posterior probability (meaning conditioning the prior distribution on the data at hand) of treatment benefit with operative treatment under various minimally clinical important difference (MCID) thresholds. The models included a dummy variable for each patient as a random intercept, an autoregressive correlation structure, and adjusted for whether the treatment was randomly assigned, the patient's pre-injury narcotic use, and a time-varying covariate that measured narcotic use at each time point. Multivariable linear regression was used to analyze the treatment effect on hospital length of stay and time to mobilization. Outcome data were missing in 16% of the sample at 2-weeks, and 14% of the sample at 6-weeks and 12-weeks, and was therefore imputed using multiple imputation for the final models [16]. To assess possible effect measure modification based on the initial degree of displacement, we stratified the sample to create two subgroups, patients with  $\geq 5$ mm of displacement and patients with  $< 5$ mm of displacement. We then calculated the average effect of operative treatment on pain in each of the subgroups. In addition, we compared the average treatment effect of operative fixation on pain with posterior-only fixation compared to operative fixation with anterior and posterior fixation. Additional sensitivity analyses recalculated the pain and function outcomes to separately compare the treatment effects between patients enrolled in the randomized cohort and the observational cohort. The analyses were performed using R Version 3.6.1 (Vienna, Austria) with the packages *lme4*, *rstan*, *brms*, and *mice*.

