
We took two critical steps to understand the potential for biased treatment estimates from pooling the results from the randomized and non-randomized participants. First, we performed sensitivity analyses to separately examine the results for the randomized and non-randomized cohorts. These analyses suggested similar (or even larger) estimated treatment benefits from surgery within the RCT data. Second, we included willingness to be randomized as a potentially confounding variable in our final analysis models, despite there being no evidence that it affected treatment.

[figure not shown]
The ability to assess the probability of different magnitudes of treatment benefit is a unique characteristic of Bayesian data analysis, and is not possible with traditional non-Bayesian statistical hypothesis testing. Despite this inherent difference in statistical principles, it should be noted that the average treatment benefits reported from our Bayesian analysis are nearly identical to the results obtained using traditional multilevel linear regression models (results not reported).

Additional results from the described analyses, that were not included in the main article, are provided below.

[figure not shown]
**Posterior probability of reduced pain.** Posterior probability of reduced pain with operative treatment within 12 weeks of injury.

[figure not shown]
**Mean pain stratified between randomized and nonrandomized patients.** The mean Brief Pain Inventory scores and 95% credible intervals within the initial 12-weeks of injury for minimally displaced complete lateral compression pelvis fracture patients. The patients are stratified based on their study type (randomized trial versus observation) and treatment type (operative versus nonoperative treatment). The pain scores are adjusted for the study type, prior narcotic use, and narcotic use at each time point.

**Posterior probability of improved function.** Posterior probability of improved function, measured with the Majeed score, with operative treatment within 12 weeks of injury.

**Mean function stratified between randomized and nonrandomized patients.** The mean Majeed scores and 95% credible intervals within the initial 12-weeks of injury for minimally displaced complete lateral compression pelvis fracture patients. The patients are stratified based on their study type (randomized trial versus observation) and treatment type (operative versus nonoperative treatment).

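### The protocol's 80% power needs a 2-week pain score from essentially all 130 patients, but 130 is also the number enrolled and no allowance is made for loss

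*Protocol*

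**What the plan says.** The sample size appears in four places in the protocol.

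- Data Analysis, the power statement: "130 patients (65 per arm) are required to have an 80% chance of detecting" a fall in the primary outcome from 5.7 to 4.56, with SD 2.3, at the 5% level.
- Description of the Study Design: "A total of 130 patients will be enrolled (65 per arm").
- Recruitment: "Approximately 130 participants will be enrolled in the Pelvis RCT study".
- Protocol Summary, Sample Size: "We will recruit a sample size of 130 patients (65 per arm) with a minimum of 2 week follow-up for the primary outcome".

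Two other sections anticipate losses after a patient joins. Under Screening and Consent, adjudication by a non-treating surgeon follows consent, and "Participants with injuries that are not judged eligible for inclusion will be withdrawn from the study". The Missing Data section lists measures to limit loss and then says "we recognize that missing data is inevitable".

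No section gives an inflation factor, a replacement rule or an enrolment figure above 130. The SAP later reports: "Outcome data were missing in 16% of the sample at 2-weeks".

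**The concern.** One number is doing two jobs. In the power statement, 130 is the number of patients whose scores enter the comparison. In the design and recruitment sections it is the number who join. The two agree only if nobody is withdrawn and nobody lacks a 2-week score, and the protocol itself says not to expect that.

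At stake is the accuracy of the stated power and detectable difference. The Data Analysis section says the trial is powered for a 20% reduction in pain at 2 weeks. If 130 is the number enrolled, any realistic loss puts power below 80% and the detectable reduction above 20%. A reader who uses the stated power to interpret a small or uncertain 2-week difference would credit the design with more sensitivity than it has.

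**Working it through.** **Inputs (protocol, Data Analysis and Randomization).** Control mean 5.7; experimental mean 4.56; difference 5.7 − 4.56 = 1.14; SD 2.3, taken as common to both arms; significance level 5%; power 80%; equal allocation. The protocol states neither the test nor its sidedness. Two-sided is inferred because it reproduces the stated 65 per arm; a one-sided normal calculation gives 51.

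**Reproducing the plan's figure.** The standardised difference is 1.14 / 2.3 = 0.496.

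- Normal approximation: n per arm = 2 × (1.960 + 0.842)² × 2.3² / 1.14² = 63.9, rounded up to 64. Power at 65 per arm is 80.7%.
- Two-sample t-test (noncentral t): n per arm = 64.87, rounded up to 65. Power at 65 per arm is 80.1%.

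The t-test gives exactly the protocol's 65, so the stated figure contains no margin beyond rounding up.

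**The first missing scores (t-test).** 65 v 65 gives 80.1%; 65 v 64 gives 79.8%; 64 v 64 gives 79.5%.

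**Wider loss.** Evaluable n per arm = 65 × (1 − loss), with loss equal in the two arms and complete cases analysed. The detectable difference is the one giving 80% power at that n, also shown as a percentage of 5.7. The last column is 65 / (1 − loss), rounded up.

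| Loss | Evaluable per arm | Power, t-test | Power, normal | Detectable difference | Enrolment per arm to keep 65 evaluable |
|---|---|---|---|---|---|
| 0% | 65 | 80.1% | 80.7% | 1.14 (20.0%) | 65 |
| 5% | 61.75 | 78.0% | 78.6% | 1.17 (20.5%) | 69 |
| 10% | 58.5 | 75.7% | 76.4% | 1.20 (21.1%) | 73 |
| 16% | 54.6 | 72.8% | 73.6% | 1.24 (21.8%) | 78 |

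The 5% and 10% rates are assumptions. The 16% is the SAP's 2-week rate, but the SAP describes "pooling the results from the randomized and non-randomized participants", so applying that rate to the randomised arms alone is also an assumption.

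**Withdrawal at adjudication as well.** Suppose 3% or 5% of patients were withdrawn after entering an arm and 10% of the rest had no 2-week score. Evaluable n is then 65 × 0.97 × 0.90 = 56.7 or 65 × 0.95 × 0.90 = 55.6 per arm, and power is 74.5% or 73.6%. Both the withdrawal rate and its timing after randomisation are assumptions.

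**The case against.** The strongest reply is that the Protocol Summary can be read as promising 130 patients who have the 2-week outcome, and that the Recruitment figure is approximate and so not a cap. On that reading there is no power shortfall, only loose wording. The reading is possible. However, the summary sets no higher recruitment target, and the design section gives 130 plainly as the number enrolled. The ambiguity is part of the problem.

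Other points have some force:

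- **Method.** Under the normal approximation 64 per arm is enough (80.1%), so one patient per arm is spare. Under the t-test a single missing score gives 79.8%, which rounds to 80%. It would be too strict to say the claim collapses at the first missing score. At 5% or 10% loss the two methods differ by less than one point.
- **Adjudication timing.** The protocol places adjudication after consent and does not say that it follows randomisation. A patient withdrawn before allocation need not reduce either arm. The 74.5% and 73.6% figures are therefore illustrative only.
- **Size.** The loss of power is about 2 points at 5% missing and 4 at 10%. A pilot SD of 2.4 instead of 2.3 would do as much (76.7% at 65 per arm). The shortfall is modest, but uncertainty in the SD is no reason to leave a foreseeable loss out of the calculation.
- **The SAP's analysis.** The SAP uses a Bayesian 12-week longitudinal model with multiple imputation and covariate adjustment, on randomised and observational patients together. It may recover precision, and the figures here do not describe its power. The protocol's power claim concerns the 2-week comparison and invokes no such gain.
- **Timing.** The data have been analysed, so enrolment cannot change, and restating power alters no estimate or interval. That limits the remedy to wording.

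**Conclusion.** The concern holds. The power statement's inputs need 64.87 patients per arm with a 2-week score. The same 65 per arm is given as enrolment, and the protocol expects losses without allowing for them. For the 2-week two-group comparison, power is 78.0% at 5% missing and 75.7% at 10%, and the detectable reduction is 20.5% or 21.1% instead of 20%. At the SAP's pooled rate of 16%, power would be about 73% and the detectable reduction 21.8%.

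This rests on reading 130 as the number enrolled, a two-sided t-test, a common SD of 2.3, loss equal in both arms and a complete-case comparison. The arithmetic is secure. The size of the shortfall depends on the loss rate, which the protocol does not give. It should be corrected, but it does not threaten the trial's conclusions.

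**What to change.** 1. In Data Analysis, name the test and its sidedness, and state that 80% power for 1.14 points assumes a 2-week score from 65 randomised patients per arm.
2. In the same place, give power and detectable difference at the expected evaluable number, with the loss rate labelled as an assumption: for example 78% and 1.17 points at 5% missing, 76% and 1.20 at 10%, and about 73% and 1.24 at 16%.
3. Make the Protocol Summary, Description of the Study Design, Recruitment and Data Analysis agree on whether 130 counts patients randomised and enrolled or patients evaluable at 2 weeks.
4. Say whether patients withdrawn at adjudication count towards the 130, and whether adjudication comes before or after randomisation.

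For the record, keeping 65 evaluable per arm would have meant enrolling 69, 73 or 78 per arm at 5%, 10% or 16% loss. The cost is wording only: no extra patients are needed and no analysis changes. The stated power becomes less favourable.

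### The pooled pain and function models do not list hospital as a term, so with two recruiting sites and a non-randomised cohort, site can confound the pooled treatment estimate

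*Protocol*

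**What the plan says.** The protocol (Description of the Study Design) names two recruiting hospitals, "University of Maryland, Shock Trauma Center and Indiana University Health Methodist Hospital", and gives no enrolment target for either. The same section adds a non-randomised cohort: "If the patient does not agree to randomization, the patient will be asked to participate in the observational arm of the study".

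Allocation is 1:1 and stratified on two factors (Protocol, Randomization): "1) patient intubation status at time of enrollment, 2) patient prescription pain medication usage during the month prior to injury". Site is not one of them.

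The SAP (Statistical Analysis) describes one set of Bayesian models for pain and for the Majeed score, fitted to both cohorts together. On structure: "The models included a dummy variable for each patient as a random intercept, an autoregressive correlation structure". On covariates, the models were "adjusted for whether the treatment was randomly assigned, the patient's pre-injury narcotic use, and a time-varying covariate that measured narcotic use at each time point". Site is not mentioned anywhere in the SAP.

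The SAP recognises that pooling may bias the estimate and reports two responses: separate analyses of each cohort, and a covariate for willingness to be randomised. For length of stay and time to mobilisation it names multivariable linear regression and lists no covariates.

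**The concern.** Leaving a centre term out of a purely randomised comparison usually costs a little precision and nothing else. This primary analysis is not purely randomised. In the observational cohort something other than chance decided who had surgery, and hospital is an obvious candidate. The protocol (Background Information) describes real disagreement over when to operate on these fractures, and Study Treatments leaves surgical technique and mobilisation to the surgeon under local standard care. Two hospitals could therefore differ in operative rate and, separately, in the pain and function their patients report. A variable related to both treatment and outcome, and absent from the model, is a confounder.

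Neither stated safeguard reaches this. The randomised yes/no term lets the two cohorts have different mean levels, but it does nothing about a site imbalance between treatments inside the observational cohort. The separate-cohort analyses are sensitivity analyses, and the pooled estimate that remains primary is unadjusted for site.

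At stake is the size of the reported benefit. The SAP reports posterior probabilities that the benefit exceeds several thresholds half a point apart, and these can move with a shift of a tenth of a point or so.

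**Working it through.** **The plan's own figure.** Protocol, Data Analysis: means 5.7 and 4.56, SD 2.3, 80% power, 5% level, 65 per arm. The difference is 5.7 − 4.56 = 1.14, which is 20% of 5.7. A two-sided two-sample t-test needs 64.87, so 65 per arm, with power 0.801. The figure reproduces. It does not depend on site, and 1.14 serves below only as a yardstick. It is a two-week design difference, whereas the SAP estimates a 12-week average.

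**Randomised cohort.** Assume 65 per arm and an even site split. The SD of the chance difference in site share between arms is √(2 × 0.25/65) = 0.088, so the 95% range is ±0.17. With an assumed 1-point site difference in pain this is at most about 0.17 point. It is random error centred on zero, not bias.

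**Observational cohort.** With site omitted,

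bias in cohort = D × G, where D is the site difference in mean pain and G = P(site A | operative) − P(site A | non-operative);

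bias in pooled estimate = D × G × w, where w is the weight of the observational cohort, because the randomised part contributes zero on average.

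The documents give none of D, G or w. Assumed: D = 0.5 to 1.0 and w = 0.5.

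- Rates 70% and 40%, equal sites: G = 0.35/0.55 − 0.15/0.45 = 0.636 − 0.333 = 0.303.
- Same rates, 90% of patients at the 70% site: G = 0.63/0.67 − 0.27/0.33 = 0.940 − 0.818 = 0.122.
- Same rates, 90% at the 40% site: G = 0.07/0.43 − 0.03/0.57 = 0.163 − 0.053 = 0.110.
- Rates 65% and 50%, equal sites: G = 0.325/0.575 − 0.175/0.425 = 0.565 − 0.412 = 0.153.

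| Operative rates | Site split | G | Bias in cohort (points) | Pooled bias, w = 0.5 (points) | Pooled bias as % of 1.14 |
|---|---|---|---|---|---|
| 70% / 40% | 50:50 | 0.303 | 0.15–0.30 | 0.08–0.15 | 7–13% |
| 70% / 40% | 90:10 | 0.110–0.122 | 0.06–0.12 | 0.03–0.06 | 2–5% |
| 65% / 50% | 50:50 | 0.153 | 0.08–0.15 | 0.04–0.08 | 3–7% |

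**Would shifts of this size show?** The SAP's displacement table gives 0.9 (95% CrI 0.1 to 1.8) for displacement below 5 mm. A normal approximation has SD (1.8 − 0.1)/3.92 = 0.434 and returns 82% for a benefit above 0.5 and 41% above 1.0, as reported. If that estimate were too high by 0.08, the corrected figures would be 77% and 34%. If too high by 0.15, they would be 72% and 28%, and the lower limit of 0.1 would fall just below zero. A bias in the other direction would raise them. The cohort mix in that subgroup is not given, so this shows sensitivity only.

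**Price of the site term.** With equal site and treatment margins, variance inflation is 1/(1 − G²): 1/(1 − 0.04) = 1.04 at G = 0.2 and 1/(1 − 0.16) = 1.19 at G = 0.4. At 130 patients and the design effect, power is then about 79% and 74%, against 81% by the same normal approximation without inflation.

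**The case against.** The best reply is the SAP's own sensitivity analysis. The randomised cohort, analysed alone, showed a benefit of surgery similar to or larger than elsewhere, and site cannot systematically confound that cohort. This stands as reassurance: nothing reported suggests that site inflated the pooled result. It does not exclude bias in either direction, and it does not adjust the primary estimate.

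The equipoise requirement (Protocol, Inclusion Criteria, item 6) also helps. Patients had to be suitable for either treatment in their surgeon's view, which limits selection by severity. It does not make two hospitals operate at the same rate or produce the same pain scores. Time-varying narcotic use may absorb part of a difference in pain management, but it is measured after treatment begins and is no clean substitute for site.

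It is also fair to say that site is only one route. Other patient and injury factors could drive the choice of surgery, and a site term leaves those untouched. Nothing in the documents shows that the two hospitals actually differ.

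A reader might go further in two ways that the documents do not support. One is to treat the absent site stratum as a flaw in the randomisation. Unstratified 1:1 allocation balances site in expectation, so the cost there is a little precision. The other is to say that length of stay and time to mobilisation are confounded by site as well. The SAP lists no covariates for those regressions, so whether site is in them cannot be determined.

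**Conclusion.** The point holds for the pooled pain and Majeed models. Two hospitals recruit, treatment in one cohort was not randomised, site is absent from the listed terms, and neither safeguard removes site confounding from the pooled estimate.

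Its size and direction are unknown. On the assumed values the pooled pain bias runs from about 0.03 to 0.15 point. A reader might take the cohort figure of 0.15 to 0.30 point as the error in the primary result. That would be wrong: it applies to the observational patients only, relies on an equal site split that gives close to the largest gap for those rates, and must be scaled by that cohort's weight. Nor do the documents support inferring that the reported benefit is a product of site. This is an inexpensive repair worth making, not a reason to set the result aside.

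**What to change.** Add site as a fixed effect to the pain and Majeed models, in the pooled analysis and in each cohort; two levels are too few for a useful random effect. Tabulate treatment by site and cohort, so that readers can judge how far site and treatment are linked. Report the site-adjusted randomised-only estimate beside the pooled one. For length of stay and time to mobilisation, state the covariates and include site.

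The cost is one parameter per model, a few lines of SAP text and a refit. Recruiting hospital should already be known for every patient, since the data system restricts each site's staff to their own participants (Protocol, Data Management). The drawback is some loss of precision if site and treatment are associated. A large loss would itself show that the unadjusted estimate was mixing the two.
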